7.3.2. Visit 2 - Safety and compliance assessment (3 months ± 7 days)

This will include the following:

Principal Investigator:	[name]	IRAS ID	252047
Short Title:	Ox-FAST Study (Oxford – Fibrates in Aortic Stenosis)	Ethics Ref:	

1. *Evaluate the participant's safety by history taking*
2. *Check medication packaging and compliance (refer to section 7.3.9)*
3. *Dispense study medication for the remaining three-month study period*

7.3.3. Visit 3 – End of treatment assessments (6 months)

Same assessments as baseline visit 1 will be undertaken:

1. *History and physical examination*
2. *Resting ECG*
3. *Venous cannulation and blood collection*
4. *CMR and MRS at 3.0T and 7.0T MRS (optional)*
5. *6 minute walk test*
6. *Cardiopulmonary exercise testing (CPET)*

Any excess medication will be returned during this visit.

7.3.4. Visit 4 – Study completion (1 month after end of treatment)

Visit 4 will mark the completion of the study for the individual participant. It is expected that this follow up will be executed via telephone call although a clinic visit may be scheduled where the patient reports any symptoms or if there are any study related concerns.

7.4. Sample Handling

Blood samples will be sent to the John Radcliffe Oxford University Hospitals (OUH) laboratory for analysis. Plasma and serum samples will be pseudo-anonymised and stored in the Division of Cardiovascular Medicine under the custodianship of the CI for the duration of the study and will be accessible to the study team for this project. De-identified samples may be used in collaboration with other organisations which may be outside the EU. No identifying information would be shared or leave the research site. De-identified samples may also be used in future ethically approved research with the consent of the participant.

Laboratory tests:

Using a cannula venous blood samples (approximately 25mls) will be collected at the time points indicated in Appendix B. Laboratory parameters to be tested are as shown below:

Principal Investigator:	[name]	IRAS ID	252047
Short Title:	Ox-FAST Study (Oxford – Fibrates in Aortic Stenosis)	Ethics Ref:	

Haematology (blood sample) 
 • Full blood count
Clinical Chemistry (fasting blood samples) 
 • Liver function tests (Albumin, ALP, ALT, bilirubin) • Renal function profile (Sodium, potassium, urea, creatinine) • Creatinine Phosphokinase (CK) – only where clinically indicated
Lipid Profile (fasting blood samples) 
 • Total cholesterol • HDL cholesterol • Calculated LDL cholesterol • Triglycerides • Free fatty acids
Pregnancy test in women of child bearing potential (WOCP) 
 • Urine sample for pregnancy test

7.5. Investigational Medicinal Product (IMP)

7.5.1. IMP description

Fenofibrate

Substance	Micronised Fenofibrate
Pharmaceutical formulation	Gelatine capsules
Source	Nottingham University hospital pharmacy
Unit strength	200mg and 67mg
Posology	1 tablet, once daily
Route of administration:	Oral

Placebo matching Fenofibrate

Substance	Placebo matching Fenofibrate
Pharmaceutical formulation	Gelatine capsules containing lactose powder
Source	Nottingham University hospital pharmacy
Unit strength	Not applicable
Posology	1 tablet, once daily
Route of administration:	Oral

Principal Investigator:	[name]	IRAS ID	252047
Short Title:	Ox-FAST Study (Oxford – Fibrates in Aortic Stenosis)	Ethics Ref:	

7.5.2. Selection of dose for the study

Fenofibrate 200 mg once daily is effective in reducing levels of triglycerides, total cholesterol, and LDL-C and increasing levels of HDL-C in patients with dyslipidemias. Its efficacy and tolerability in the treatment of hypertriglyceridemia and combined hyperlipidemia have been demonstrated in numerous clinical trials.^{22,23} As a PPAR α agonist, it has been shown to regulate cellular lipid metabolism and have protective cardiovascular effects.²⁴⁻²⁷ These modes of action support the scientific rationale of using fenofibrate in this study and 200mg once daily is the recommended initial adult dose. In elderly patients without renal impairment, the normal adult dose is recommended. In renal dysfunction, the dose of fenofibrate may need to be reduced. Our recruitment criteria will exclude patients with eGFR<30ml/min. In patients with eGFR 30-59ml/min, the BNF recommended dose of 67mg daily will be administered. Nottingham University hospital (NUH) pharmacy will supply both 200mg and 67mg dose preparations to the local pharmacy. Patients will be randomised in a double blind fashion to receive either placebo or active drug (fenofibrate dose based on eGFR) by the local pharmacy as explained in section 7.5.3. Patients renal functions will be assessed at the beginning and end of the study as mentioned in section 7.4.

7.5.3. Randomisation, blinding and code-breaking

- Randomisation and Blinding: Nottingham University hospital (NUH) pharmacy will supply both the active drug and placebo bottles, with annex 13 (EU guidelines to Good Manufacturing Practice) compliant labels containing a sequential pack number according to randomisation list, to the site pharmacy. The small tear off section on the bottle stating whether the product is active or placebo will be removed at the point of dispensing by the site pharmacy and attached to an accountability log as proof of which product the patient has been administered. The local pharmacy will also be made aware of patient's eGFR thus enabling them to dispense the correct dose of the active drug. Hence, with the exception of the site pharmacy, all patients, investigators and everyone else involved in study conduct/analysis or with any other interest in this double-blind study will remain blinded with regard to the randomised treatment cohort until all patients have completed the study and database lock has taken place. The randomisation code will be kept secret by the site pharmacy until the database lock.
- Generation of the allocation sequence: This will be generated by the Nottingham university pharmacy using website randomization.com and they will supply a list to the site pharmacy,

Principal Investigator:	[name]	IRAS ID	252047
Short Title:	Ox-FAST Study (Oxford – Fibrates in Aortic Stenosis)	Ethics Ref:	

who will be unblinded. Participants will be enrolled and assigned to the intervention/study arm by site pharmacy based on this randomisation list.

- **Code-breaking:** Code break envelopes will be provided by Nottingham University Pharmacy for each participant number according to the randomisation list to the site pharmacy. Emergency unblinding will be available to study investigators or clinical teams via site pharmacy 24 hours a day, 7 days a week, but will only be used in an emergency situation when the identity of the study drug must be known to the investigator/participant's clinical team in order to provide appropriate medical treatment or otherwise assure safety of study participants. Whenever possible and if time allows, the need for unblinding will be discussed with the CI before the unblinding of study medication takes place. The reason for unblinding will be documented in the source documents along with the date and the initials of the person who broke the code. If unblinded, the participant may continue in the study as planned, unless in the opinion of the investigator there is a reason why the participant must discontinue.

7.5.4. Supply of IMP

Study medication will be assigned via flagged labels at randomisation and dispensed in a double-blind manner. At Visit 1 the patient will be dispensed sufficient medication for three-month treatment period. Further dispensing for rest of the treatment period will occur on visit 2. In the event that the patient requires replacement medication, extra dispensing will be arranged.

From the start of the treatment period patients will be instructed to take the study medication once daily with a glass of water. Fenofibrate should be taken with food. To ensure a dose interval of about 24 hours, the medication should be taken in the morning at approximately the same time every day. If a dose is missed by more than 12 hours, that dose should be skipped and the next dose should be taken as scheduled. No double doses should be taken. On the day of Visit 2 and Visit 3 the dose should be taken at the usual scheduled time, regardless of the timing of assessments. Daily dosing should continue until the day of Visit 3, when the last dose is taken.

To allow for any delay in scheduling Visit 3 whilst avoiding bias (since half-life of fenofibrate ranges from 10 to 35 hours) patients will be provided with sufficient extra medication.

In extenuating circumstances, IMP may be provided to participants by courier or other secure delivery method for example via a nominated person. Participants will be asked to

Principal Investigator:	[name]	IRAS ID	252047
Short Title:	Ox-FAST Study (Oxford – Fibrates in Aortic Stenosis)	Ethics Ref:	

provide verbal consent to providing contact details for shipping purposes and for a nominated person to deliver. Participants may also return IMP to the research team this way, for example if they are withdrawn from the study.

7.5.5. Packaging, labelling and re-supply

Active 200mg Fenofibrate capsules will be removed from their original blister pack and placed into an empty hard shell gelatine capsule. The capsule will then be back filled with lactose powder to prevent the capsule moving inside the capsule shell. These capsules will then be packed into bottles, each containing 30 capsules.

Matching placebo capsules will be manufactured using the matching capsule shells and packed into bottles in the same quantities described above. 294 bottles containing 30 X 200mg fenofibrate capsules over-encapsulated into suitably sized capsules and back filled as required for the 49 treatment group patients, and 78 bottles containing 30 X matching colour placebo capsules adequate for the 13 patients in the placebo group will be supplied. This is sufficient for the duration of the study.

The investigational products will be provided by Nottingham University pharmacy. They will be manufactured, packaged and labelled in accordance with the principles of Good Manufacturing Practice (GMP). Re-supply to the site will be managed by the study team in collaboration with site pharmacy, which will also monitor expiry dates of supplies available at the site.

7.5.6. Storage Conditions

Drug supplies will be kept in their original packaging and in a secure limited access storage area in accordance with site pharmacy SOPs and the recommended storage conditions on the medication label. A temperature log will be maintained for documentation. If the storage conditions are found to be outside the specified range, the process outlined in site pharmacy SOPs will be followed.

7.5.7. Accountability of trial treatments

The pharmacist and/or investigational drug storage manager at site pharmacy will receive the investigational drugs delivered by the sponsor or delegate when the following requirements are fulfilled:

Principal Investigator:	[name]	IRAS ID	252047
Short Title:	Ox-FAST Study (Oxford – Fibrates in Aortic Stenosis)	Ethics Ref:	

- Approval of the clinical study protocol by the ethics committee;
- Availability of a signed and dated study contract between the sponsor and the investigational site,
- Approval/notification of the regulatory authority, e.g. competent authority,
- Availability of the curriculum vitae of the Principal Investigator,
- Availability of a signed and dated study protocol,
- Availability of the proof of a medical license for the Principal Investigator

Investigational drugs are not allowed to be used outside the context of this protocol. Patients should be instructed to return unused investigational drug.

The investigator and/or pharmacist and/or investigational drug storage manager will maintain records of the product's delivery to the study site, the inventory at the site, the use by each patient, and the disposal of unused products. If applicable, the sponsor or drug distribution centre will maintain records of the disposal. These records will include dates, quantities, batch/serial numbers, expiry ('use-by') dates, and the unique code numbers assigned to the investigational product and study patients. The investigator/pharmacist/investigational drug storage manager will maintain records that document adequately that the patients were provided the doses specified by the study protocol and reconcile all investigational products received from the sponsor. At the time of returning investigational product to the site pharmacy pharmacist/investigational drug storage manager must verify that all unused or partially used drug supplies have been returned by the study patients and that no supplies will remain in the investigator's possession.

7.5.8. Concomitant medication

Fenofibrate is approved for treatment of hypercholesterolemia and is relatively safe with most of the medications. Common known drug interactions include those with warfarin and statins. Patients already on warfarin may need their dose adjusted based on their INR. Such patients and their GP's will be given all relevant information and advice. Concomitant use of statins and fenofibrate can increase risk of myopathy in certain patients. Patients will be monitored throughout the study for any such symptoms and blood levels for CK will be checked where indicated. Accordingly, necessary dose adjustment/action will be taken. Other drug interactions, if any, with participant's concomitant medications will be checked to ensure safety. To eliminate confounding bias, only those participants who have been stable on their current regular medications for at least six weeks prior to the entry to the study will be recruited.

Principal Investigator:	[name]	IRAS ID	252047
Short Title:	Ox-FAST Study (Oxford – Fibrates in Aortic Stenosis)	Ethics Ref:	

Participants will be provided with study specific telephone number to contact if they have any issues or concerns.

7.5.9. Compliance with study medication

Patients will be requested to bring all remaining study medication including empty package material with them when attending visits. Based on tablet counts, treatment compliance will be calculated as shown in the formula below.

$$\text{Treatment compliance (\%)} = 100 \times \frac{\text{Number of tablets actually taken}}{\text{Number of tablets which should have been taken}}$$

Compliance should be between 80% and 120%. If the number of doses taken is not between 80-120%, site staff will explain to the patient the importance of treatment compliance. If the assessment of compliance at Visit 3 indicates a compliance of less than 80%, the investigator may decide to perform limited Visit 3 assessments as the patient will not be used for the primary analysis.

7.5.10. Post study treatment

There is no indication or requirement for any post study treatment in this study

7.6. Discontinuation/Withdrawal of Participants from Study

Each participant has the right to withdraw from the study at any time. In addition, the Investigator may discontinue a participant from the study at any time if the Investigator considers it necessary for any reason including:

- Pregnancy
- Ineligibility (either arising during the study or retrospectively having been overlooked at screening)
- Significant protocol deviation
- Significant non-compliance with treatment regimen or study requirements
- Withdrawal of Consent
- Loss to follow up

Principal Investigator:	[name]	IRAS ID	252047
Short Title:	Ox-FAST Study (Oxford – Fibrates in Aortic Stenosis)	Ethics Ref:	

Withdrawal from the study will not necessarily result in exclusion of the data for that participant from analysis. Withdrawn participants will be replaced. The reason for withdrawal will be recorded in the CRF.

Patients will receive follow-up phone call one month post completion of study to check for any side-effects from the study medication or any other issues.

7.7. Definition of End of Study

The end of study is the date of the last analysis of the last sample.

8. INTERVENTIONS

The study will investigate the effect of fenofibrate on myocardial lipid content in patients with asymptomatic moderate to severe aortic stenosis. All subjects will be randomised such that 49 patients receive fenofibrate 200mg once daily and 13 patients receive matching placebo tablets for 6 months +/- 1 month in a double-blind randomized parallel design. Outcome measures will be assessed at baseline and at the end of 6 months. For detailed information on IMP, refer to section 7.5.

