- Group 1: This will include forty-nine patients who will receive treatment with fenofibrate for six months duration.
- Group 2: This group will act as controls, comprising of thirteen patients who will be randomly assigned to receive placebo for six months duration.

The study will be conducted in a single centre specialising in cardiac imaging. Both groups of patients will be identified from the large pool of outpatient clinics at John Radcliffe Hospital (Oxford) and district general hospitals in the region. Patients with asymptomatic moderate to severe aortic stenosis not planned for AVR or transcatheter aortic valve implantation (TAVI) will be reviewed against the eligibility criteria and invited to participate in the study.

Based on previous studies it is estimated that approximately 100 patients will need to be reviewed in total in order to identify 62 eligible patients. Vetting will continue until eligible patients have been randomised into both groups. A log of all participants recruited into the study will be maintained in the investigator site file (ISF) at the investigational site irrespective of whether they have been treated with investigational drug or not. Re-screening of patients who do not meet the inclusion/exclusion criteria will not be permitted, however assessments may be repeated within the screening period and the latest assessment prior to randomisation must always be used to assess eligibility.

Principal Investigator:	[name]	IRAS ID	252047
Short Title:	Ox-FAST Study (Oxford – Fibrates in Aortic Stenosis)	Ethics Ref:	

Subsequently, all eligible patients will undergo informed consent and baseline tests - bloods will be drawn for lipid profile, renal and liver function, glucose and free fatty acids, and urine for pregnancy test in women of child bearing potential. ¹H-MRS to assess MTG, ³¹P-MRS to assess myocardial energetics (PCr/ATP), standard cardiac magnetic resonance imaging to assess LV strain and LV mass, late gadolinium enhancement (fibrosis), physiological exercise assessments to measure VO₂ max and 6 minute walking distance. Patients will then be randomly assigned in a double blind fashion to either receive fenofibrate 200mg once daily or placebo. Randomisation will be done by local pharmacy using randomisation code list provided by Nottingham pharmacy. The subject and study investigators will be blinded to the randomisation schedule.

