6.3. Exclusion Criteria

The participant may not enter the study if ANY of the following apply:

- Known coronary artery disease, history of angina, myocardial infarction or presence of regional wall motion abnormalities
- Presence of other underlying cardiomyopathy
- Left ventricular EF<50%
- Presence of uncontrolled hypertension
- Presence of type 1 or type 2 diabetes mellitus
- Presence of liver impairment
- Female participant who is pregnant, lactating or planning pregnancy during the course of the study
- BMI >40 kg/m²
- Significantly impaired renal function (eGFR<30ml/min)
- Intolerance to or concurrent use of fibrates or PPAR α agonists.
- Contraindications to CMR imaging (implantable devices or other metal implants, internal cardioverter-defibrillator, cranial aneurysm clips, metallic ocular foreign bodies, hypersensitivity to gadolinium)
- Inability to tolerate MRI scanning (claustrophobia, inability to lie flat)
- Any other significant disease or disorder which, in the opinion of the investigator, may either put the participant at risk because of participation in the study, or may influence the result of the study, or the participant's ability to participate.

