10.3. Analysis of Outcome Measures

Based on literature data, the primary endpoint of change from baseline in MTG is regarded as normally distributed. The change from baseline of MTG after 6 months of treatment will therefore be analysed by paired student's t-test. The primary objective will be addressed by a one-sided test at level $\alpha = 0.05$. For continuous exploratory endpoints, the same model as the primary one will be used.

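### The protocol states two different active regimens (200mg for all 49 patients, or a strength set by eGFR), and the supply, sizing and analysis sections recognise only one strength

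*Combined protocol and SAP*

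**What the plan says.** Two accounts of the active arm run through the protocol.

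**One strength.** Section 8: "All subjects will be randomised such that 49 patients receive fenofibrate 200mg once daily". Section 5: "Patients will then be randomly assigned in a double blind fashion to either receive fenofibrate 200mg once daily or placebo". Neither mentions eGFR. Section 7.5.5 provides 294 bottles of 30 over-encapsulated 200mg capsules for the 49 treated patients and calls the supply enough for the whole study. It gives no quantity of 67mg bottles and describes no over-encapsulation of that strength.

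**Two strengths.** Section 7.5.1 lists unit strengths of "200mg and 67mg". Section 7.5.2 says "In patients with eGFR 30-59ml/min, the BNF recommended dose of 67mg daily will be administered", states that both preparations will be supplied, and describes the randomised contrast as placebo against active drug with the dose depending on eGFR. Section 7.5.3 adds: "The local pharmacy will also be made aware of patient's eGFR thus enabling them to dispense the correct dose of the active drug". Section 14.2 repeats that participants with low eGFR get a reduced dose. The renal exclusion in 6.3 is only "Significantly impaired renal function (eGFR<30ml/min"), so the 30-59 band can be recruited.

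**Statistics.** Sections 10.1 and 10.2 size the treatment group on one mean change of 0.15% with SD 0.36. Section 10.3 says "The change from baseline of MTG after 6 months of treatment will therefore be analysed by paired student's t-test", one-sided at 0.05. None of these sections mentions strength or eGFR.

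**The concern.** For an active patient with an eGFR of, say, 45, sections 5 and 8 give one daily dose and section 7.5.2 gives another. The pharmacy, the investigators and the eventual report could each follow a different section. The supply figures make this practical as well as editorial, because the only stated quantity of active drug covers every treated patient at 200mg.

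The statistical consequence concerns what the primary result estimates. The trial rests on the within-arm change in the fenofibrate group, so the definition of that arm is the definition of the treatment being estimated. If some patients take 67mg and its effect on myocardial triglyceride is smaller, the pooled mean change is pulled towards zero, and a null result could partly reflect the mix of strengths. If the result is positive, a reader of sections 5 and 8 could take it as a result for 200mg. As planned, no display would show whether the change differs by strength.

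**Working it through.** **1. Supply against dose rule.** Six bottles of 30 capsules per patient gives 49 × 6 = 294 active bottles and 13 × 6 = 78 placebo bottles, exactly the figures in 7.5.5. All 294 active bottles are 200mg. Section 7.5.5 therefore follows sections 5 and 8, while 7.5.1, 7.5.2, 7.5.3 and 14.2 follow the two-strength rule.

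**2. Reproducing the plan's sample size.** Inputs: change 0.15, SD 0.36, power 80% (section 10.2); one-sided 0.05, paired t-test (section 10.3). With the non-central t distribution:

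- n = 38: noncentrality = (0.15 / 0.36) × √38 = 2.569; critical value t(0.95, 37 df) = 1.687; power 81.0%.
- n = 37: power 79.997%, just under 80%.

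The stated minimum of 38 is reproduced. For dropout, 38 / 0.77 = 49.35, which rounds up to 50; the stated 49 is one fewer.

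**3. What a second strength could do.** Two quantities are needed that the documents do not give, so both are assumptions: p, the share of active patients on 67mg, and f, the 67mg effect as a fraction of the 200mg effect. The 200mg effect is taken as the planned 0.15.

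- Pooled mean change = 0.15 × [(1 − p) + p × f]
- Pooled SD = √{0.36² + p(1 − p) × [0.15 × (1 − f)]²}

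Three values of f are used: 1 (equal effect), 67/200 = 0.335 (proportional to milligrams) and 0 (no effect at 67mg).

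Example with p = 0.20 and f = 0.335: mean = 0.15 × (0.80 + 0.067) = 0.130; variance = 0.1296 + 0.16 × 0.09975² = 0.1312, so SD = 0.362; noncentrality = (0.130 / 0.362) × √38 = 2.21; power 70.1%.

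Power at n = 38, one-sided 0.05:

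| Assumed share on 67mg | Equal effect | Proportional to mg | No effect at 67mg |
|---|---|---|---|
| 5% | 81.0% | 78.5% | 77.0% |
| 10% | 81.0% | 75.8% | 72.8% |
| 20% | 81.0% | 70.1% | 63.5% |
| 30% | 81.0% | 64.0% | 53.5% |
| 40% | 81.0% | 57.5% | 43.5% |

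The number of evaluable patients needed for 80% power would be 43, 50 and 58 at shares of 10%, 20% and 30% under proportionality, and 47, 59 and 77 if 67mg had no effect.

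**The case against.** The best defence is that sections 5 and 8 are summaries. Section 8 ends "For detailed information on IMP, refer to section 7.5", and 7.5.2 gives the full rule. The objectives and hypothesis name fenofibrate without a dose. On this reading there is one regimen, dosed by eGFR, and only the summaries are loose. Part of this stands: a coherent intended regimen can be read from 7.5.2 and 7.5.3. But the pointer does not settle the matter, because 7.5 is itself divided: 7.5.5 supplies the whole active arm at 200mg. Separate 67mg stock may be intended, since 7.5.2 says both preparations will be supplied, but no quantity is stated.

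It is also fair to object that the power figures rest on two unknowns. A dose lowered because of renal dysfunction need not have a proportionally lower effect, and a small share on 67mg would cost little. That stands in full.

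A reader might infer several stronger criticisms that the documents do not support:

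- *That the pooled result describes neither regimen.* It would describe fenofibrate dosed by eGFR, which is how 7.5.2 defines the active arm. It would not be a clean estimate for either strength alone.
- *That nothing downstream recognises the second strength.* Dispensing in 7.5.3 and the risk section 14.2 both do; the gap is in supply, sizing and analysis.
- *That the lack of eGFR strata harms the primary result through placebo imbalance.* The primary test is within the active arm, and 10.1 says the placebo comparison is not part of the calculation. Strata would also achieve little: with 6 or 12 of 62 patients in the band, the expected placebo number is 13 × 6/62 = 1.3 or 13 × 12/62 = 2.5.
- *That the compliance rule in 7.5.9 is inconsistent because a partly compliant 200mg patient may take more milligrams than a fully compliant 67mg patient.* The rule measures adherence to the assigned capsules, and the comparison presumes that raw milligrams are the relevant exposure across levels of renal function.

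**Conclusion.** The contradiction is established from the text alone: sections 5, 8 and 7.5.5 cannot all stand alongside 7.5.1, 7.5.2, 7.5.3 and 14.2 for an eligible patient with eGFR 30-59. It affects conduct as well as wording.

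The effect on the primary result is conditional. Power ranges from no loss (81%) to 64% under proportionality, or 54% with no effect at 67mg, at an assumed 30% share. The range assumes that 0.15 is the 200mg effect and that exactly 38 patients are evaluable. The stated 38 is not wrong in itself; it simply has no dose component. No view is taken here on which dose rule is right.

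**What to change.** Reconcile sections 5, 8 and 7.5.5 with 7.5.1, 7.5.2, 7.5.3 and 14.2, so that a single definition of the active regimen, with supply quantities and capsule preparation to match, applies throughout. Which definition is for the sponsor to decide.

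If two strengths remain:

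- state in section 10 that the primary estimate is for fenofibrate dosed by eGFR;
- report the primary change in myocardial triglyceride, with estimate and interval, by assigned strength;
- add a sensitivity analysis restricted to patients assigned 200mg;
- word the conclusion to match the regimen actually studied.

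The cost is protocol wording, a revised supply statement, one extra table and one sensitivity analysis. No patients or visits are added. The limitation is that the 67mg estimate will be imprecise and, because strength is set by eGFR, cannot be separated from renal function. It should be presented as descriptive.
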